Aim 1: To determine how the dose of DHA (1000 mg vs 200 mg/day) during pregnancy interacts with GWG (excessive vs appropriate) to influence total infant FM at 24 months of age. We propose a novel nutritional approach to test the effect of DHA on infant FM. In the parent trial, pregnant women are randomized to daily capsules that provide 1000 or 200 mg DHA/day. All of these pregnant women will experience GWG, some at the appropriate level and some at the excessive level. Offspring exposed to excessive GWG have greater FM than offspring exposed to appropriate GWG. We believe there is an opportunity for DHA to influence FM in infants exposed to excessive GWG. Preliminary data suggest that DHA may protect against excess infant FM. We will test if the mean difference in total infant FM at 24

months of age is greater in infants exposed to excessive GWG and high vs. low DHA compared to infants exposed to appropriate GWG and high vs. low DHA.

Aim 2: To explore how dose of DHA (1000 mg vs 200 mg/day) may interact during pregnancy to influence central FM at 24 months of age. We will explore the interaction with variables including GWG and gender.

Impact: This data will address a gap in knowledge about how improving maternal DHA status might mitigate excess offspring fat accumulation in response to the stress of excessive GWG. The results of this proposal could lead to evidence-based guidelines for DHA requirement in pregnancy.

RESEARCH STRATEGY A) **SIGNIFICANCE**

A1) **Solutions are needed**: The obesity statistics stabilized over the last decade but remain high with a detrimental health impact. Currently 35% of adults are overweight and 35% are obese and 17% of 2-19 year olds are obese¹. Maternal obesity is related to greater central FM in newborns^{2,3}. FM location in adults⁴ and children^{5,6} is an important driver of disease risk and development. Centrally located fat, especially visceral adipose tissue (AT), in adults is greater in individuals with type 2 diabetes when compared to those without diabetes⁷ whereas AT located in the femoral-gluteal region (hips and legs) is cardioprotective⁸. Interventions to prevent the evolution of obesity, including improvements in nutrient intake that result in a cardioprotective AT pattern are desperately needed.

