A7) **DHA and offspring body composition**: Observational studies have measured maternal DHA status during pregnancy and looked for differences in body composition and AT deposition in the offspring. Sanz et al.²⁴ measured maternal red blood cell (RBC) DHA at 2-days postpartum and assessed infant body composition using dual energy x-ray absorptiometry (DXA) at 2 weeks and 4 months. At 2 weeks but not at 4 months, they found an inverse correlation between maternal DHA levels and offspring abdominal FM (r=-0.51; p=0.003). Donahue et al.⁷⁵ measured maternal RBC fatty acids late in pregnancy and offspring skinfolds at 3 years old in the Project Viva cohort. They found an inverse association between maternal n-3 LCPUFA status (DHA and eicosapentaenoic acid (EPA, 20:5n-3) and the sum of offspring triceps and subscapular skinfolds. Data from the Southampton Women's Survey²⁶ measured maternal RBC PUFA status late in pregnancy and measured offspring body composition using DXA at 4 and 6 years old. They found a positive correlation between maternal RBC total n-3 and offspring FFM at 4 and 6 years old (β =0.11; p=0.06 and β =0.14; p=0.02, respectively). Data were not reported for AT distribution. Vidakovic et al.²⁷ measured maternal RBC PUFA status mid-pregnancy and used DXA to measure offspring body composition and distribution at 6 years old. They associated greater maternal DHA with lower offspring FM and android to gynoid FM ratio (a measure of central to peripheral FM). Even though relationships were found with FM, no relationships were found between maternal DHA and offspring BMI. This suggests BMI is not a sensitive marker of fat deposition early in development.

A8) **DHA RCTs where body composition is not the primary outcome:** Multiple RCTs have been completed where DHA is prenatally and/or postnatally supplemented and the

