[name] will provide initial and ongoing training for all Research Assistants regarding assessment of body composition. All Research Assistant's will undergo standardized body composition training and annually, re-fresher training will be completed. For quality control purposes, daily scans will be performed on the DXA system using the Quality Assurance block provided by the manufacturer to simulate fat and fat-free soft tissues, respectively^{119,120}. Movement is not tolerated by the DXA system however total body scans in newborns and toddlers are relatively short (~3 minutes). Co-I [name] has considerable experience (n=1,540 scans from birth to 6 years old) obtaining DXA images in infants, toddlers, and children. She will be in charge of assisting [name] to develop protocols to ensure a valid DXA scan is captured at each age time point.

D5) **Assessments**: Infant body composition and AT distribution will be measured at 2 weeks and 6, 12, and 24 months using dual energy x-ray absorptiometry (DXA). Collection and analysis of maternal RBC will be completed as part of the parent RCT. Maternal blood will be collected at delivery and analysis will be completed after delivery. Upon completion of this protocol, [name] will have access to study assignment (1,000 mg/d or 200 mg/d). An overview of study visits is listed in **Table 5**.

Table 5. An outline of study visits and procedures.					
Study procedure	2 wks	6 months	12 months	24 months	
Enrollment & Consent	Prior to any study visit				
DXA scan	•	•	•	•	
PeaPod	•	•			
Anthropometry & skinfolds	•	•	•	•	
Diet recall & questionnaires	•	•	•	•	
Incentives	\$125	\$125	\$125	\$125	

D5a) Dual energy x-ray absorptiometry to measure total body fat and AT distribution: Dual energy x-ray absorptiometry (DXA; Prodigy, Madison, WI, encore software version 13.60) will be used to measure body composition and regional AT distribution. The DXA is located within the Dietetics & Nutrition Clinic inside the Smith West building at KUMC. Using specific anatomic landmarks as previously described, regions including the arms, legs and trunk will be demarcated⁸. Calculations for FM in each region and summed for regions comprising the central (trunk) and peripheral (arms plus legs) will be completed. If a child moves during the scan the scan may need to be re-done but no more than 8 total scans will be given over the duration of the study.

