Recruitment/screening							
Data collection							
Data collection							
Data entry							
Data collection ends							
Data analysis and							
writing							
Manuscript prep &							
submission							

D6) **Study timeline**: Listed in **Table 6** is the timeline for the study.

D7): **Statistical analyses**: The primary purpose of this study is to determine if there are differences in the offspring FM at 24 months when exposed prenatally to high vs. low DHA supplementation and if maternal GWG status impacts this relationship (appropriate or excessive GWG).

D7a) **Aim 1 analysis:** Using a two-way analysis of variance (ANOVA) on the 24 months FM, we will test for a statistical interaction between GWG group and DHA dose. The specific interaction from this ANOVA will test the contrast to **investigate if the supplement of 1000 mg DHA/day compared to 200 mg DHA/day during pregnancy can reduce infant FM at 24 months and specifically if this reduction is greater in offspring exposed to excessive GWG versus appropriate GWG.** A two sided t-test statistic (alpha=0.05) is calculated from the appropriate contrast from the two-way ANOVA (GWG and DHA).

D7b) **Aim 2 analysis:** A three-way analysis of variance (ANOVA) on the 2 year central FM, we will test for a statistical interaction between both GWG and DHA dose and offspring gender and DHA dose.

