D7c) **Longitudinal analysis:** Additionally, we will perform a linear mixed model to explore differences between the high vs. low supplement groups for infant FM and distribution. The dependent variable will be infant FM or infant central FM and the independent variable will be DHA group (fixed effect) and time (4 visits: 2 wks, and 6, 12, and 24 months). The model will include the fixed effects of treatment, time and the treatment-time interaction, with the subject effect treated as random to account for the dependence among repeated observations. This analysis allows for unbalanced data (allows for missing data). We will use exploratory analyses to investigate, in a univariate fashion, covariates. GWG and infant gender will be included as well as other potential covariates including parity, maternal age, pre-pregnancy BMI, parity, education level, maternal diet, infant diet, infant age at test, gestational age at birth, and socioeconomic status. An auto-regressive covariance structure will account for unevenly spaced visits. For missing outcome data, the data vector will be used to impute the missing value. Infant gender will be explored both as a confounder and as an effect modifier to account for differences in growth rates. We will analyze the data without confounding variables and repeat the analysis with confounding variables.

D7d) **Power calculation:** We performed a power analysis based on pilot data reported in **Table 2**. We calculated a total of n=120 would be required to answer the primary aim. Of the total n=120, we anticipate n=54 will experience appropriate GWG (45%) and n=66 will experience excessive GWG (55%) with each approximately equally allocated to low and high DHA supplementation groups. For the given effect size (population mean differences of -168 vs 304 grams), the power is 0.815. This means that 81.5% of studies would be expected to yield a significant effect to detect an interaction, rejecting the null hypothesis that the two population means are equal. The test is two-sided. Allowing for 33% attrition, this increases the sample size to n=180. To answer the primary aim in a second group of Spanish speaking subjects, we will increase the sample size by n=180 for a total sample of n=360.

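### The longitudinal analysis (D7c) names fat distribution as a target but measures only absolute central fat mass, so a uniform fall in fat could be misread as a change in fat pattern

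*Combined protocol and SAP*

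**What the plan says.** D7c states its purpose as to "explore differences between the high vs. low supplement groups for infant FM and distribution". The next sentence gives the outcomes: "The dependent variable will be infant FM or infant central FM and the independent variable will be DHA group". The fixed effects are treatment, time and their interaction. GWG and infant gender are to be included, with "other potential covariates including parity, maternal age, pre-pregnancy BMI, parity, education level, maternal diet, infant diet, infant age at test" and others. That list is open, but it names no total FM, peripheral FM, weight or length.

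D7b plans "A three-way analysis of variance (ANOVA) on the 2 year central FM" and tests GWG x DHA and gender x DHA. It names no covariate.

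The Specific Aims word Aim 2 as exploratory: "To explore how dose of DHA (1000 mg vs 200 mg/day) may interact during pregnancy to influence" central FM at 24 months. Aim 2 does not mention distribution.

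D5a, whose heading covers total fat and its distribution, already provides the parts of a relative measure: "Calculations for FM in each region and summed for regions comprising the central (trunk) and peripheral (arms plus legs) will be completed". D5d defines a second central FM, an index built from three skinfolds. D7 does not say which of the two it means.

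Elsewhere, the project objective in the Specific Aims includes adipose tissue distribution, and the Innovation paragraph presents it as unexplored for maternal DHA supplementation. The footnote to pilot Table 3 labels central FM the distribution variable.

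**The concern.** Distribution means where fat lies relative to the rest of the body. Section A1 rests on that contrast: central fat is described as harmful, and hip and leg fat as cardioprotective. An absolute amount of trunk fat cannot express it. If every region shrinks by the same percentage, trunk FM falls by that percentage and the pattern does not change.

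Aim 1 hypothesises a fall in total FM. If that hypothesis is true, central FM will tend to fall as well, whether or not DHA affects location. The analysis D7c presents as bearing on distribution would then partly repeat the total FM result on a component of it. At stake is the interpretation of the distribution findings: a general reduction in fat could be taken as evidence that DHA changes where fat is laid down.

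**Working it through.** **The plan's own figure.** The documents give no power for Aim 2 or D7c. The only power figure is 0.815 in D7d, for the Aim 1 interaction at n=120. I use it only to choose the effect sizes below.

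**Inputs from the documents**
- Cells at n=120 (D7d): 54 appropriate and 66 excessive GWG, about equally split by dose, giving 27/27/33/33.
- SDs of change in FM (Table 2): 549.9, 622.4, 640.7 and 539.3 g. Root mean square about 590 g.
- Contrast from the D7d figures: 304 - (-168) = 472 g.
- Contrast from the Table 2 means, low minus high DHA: excessive 1499.0 - 1026.4 = 472.6 g; appropriate 1189.5 - 1330.4 = -140.9 g; interaction 472.6 + 140.9 = 613.5 g.
- n=240: 360 enrolled less 33% attrition, doubling each cell, if the two language groups are analysed together.

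**Assumption not in the documents:** a correlation r of 0.80-0.95 between central and total FM.

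**Step 1: check against 0.815.** SE = 590 x sqrt(1/27 + 1/27 + 1/33 + 1/33) = 590 x 0.367 = 216.5 g. Two-sided 5% power on total FM is 0.58 for 472 g and 0.80 for 613.5 g. The effect stated in D7d does not reproduce 0.815; the Table 2 contrast nearly does. That is a separate matter, but it is why both contrasts are carried forward.

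**Step 2: effect on central FM with no redistribution.** Let central FM = share x total FM, with the share unrelated to dose and to total FM. The standardised effect on central FM is then r times that on total FM. The noncentrality is r x contrast / SE, for example 0.80 x 472 / 216.5 = 1.74 and 0.95 x 613.5 / 216.5 = 2.69. At n=240 the SE is 153.1 g.

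| Contrast on total FM | n=120, r = 0.80 to 0.95 | n=240, r = 0.80 to 0.95 |
|---|---|---|
| 472 g | 0.41 to 0.54 | 0.69 to 0.83 |
| 613.5 g | 0.61 to 0.76 | 0.89 to 0.97 |

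These are chances of a significant GWG x DHA interaction on central FM although the fat pattern is unchanged.

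**Step 3: D7c, one-visit stand-in.** Averaging the Table 2 dose differences over GWG gives 0.55 x 472.6 - 0.45 x 140.9 = 197 g. With 60 per dose group, a test of dose on central FM is significant in about 30-40% of trials under the same r. If DHA has no effect in appropriate GWG, the average is 0.55 x 472.6 = 260 g and the range is 48-62%.

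**Step 4: would a relative measure behave?** Simulation with assumed mean FM 2500 g, CV 25%, and trunk share 30-40% with SD 3 points, the same in both dose groups:
- Uniform 15% reduction, 60 per dose group: absolute trunk FM significant in 91-92% of trials, trunk/total share in about 5%, trunk FM adjusted for total FM in about 4%.
- Uniform 20% reduction in the excessive-GWG, high-DHA cell only, interaction test at a share of 35%: absolute trunk FM significant in 57% (n=120) and 85% (n=240), share in about 5% at both.

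In grams, a uniform loss of 472 g lowers trunk FM by 472 x 0.30 = 142 g to 472 x 0.40 = 189 g with no change in pattern.

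**The case against.** The strongest reply is that Aim 2 does what it says. It names central FM, D7b analyses central FM, and the Specific Aims and A1 link central fat itself to disease. This stands. A reader might infer that Aim 2 uses the wrong outcome or claims to test distribution; its wording does neither. The mismatch is in D7c, reinforced by the D5a heading, the pilot footnote and the stated objective.

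A reader might also infer that a uniformly leaner child would necessarily be reported as having a changed fat pattern. The documents contain no such reporting rule. Total FM is analysed in D7a and in D7c, peripheral FM is calculated, and the covariate list is open, so a careful author could see a parallel fall. The defensible word is "could". Even so, setting a result on total FM beside one on central FM is not a test of pattern: a difference in significance between the two does not show that the trunk changed more than the limbs.

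A7 should not be over-read. It describes one cited observational study's "android to gynoid FM ratio (a measure of central to peripheral FM"). It does not adopt that ratio for this study, and android/gynoid is not trunk over arms plus legs.

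On size, a simple two-group comparison within excessive GWG gives 74-87% at 33 per arm and 96-99% at 66 per arm under the same correlations. D7 plans no such test on central FM, so those figures overstate the problem for the planned interaction.

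Finally, both analyses are exploratory and a ratio could be derived later from stored regional data. That is true, but choosing among ratio, share and adjusted analysis after seeing results is what pre-specification avoids.

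**Conclusion.** The concern holds in a limited form. D7c promises an analysis of distribution and provides only an absolute amount, and nothing in D7 separates general leanness from a changed pattern. If DHA lowers FM uniformly, the planned GWG x DHA interaction on central FM would be significant in about 41-76% of trials at n=120 and 69-97% at n=240 with no redistribution.

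Those ranges rest on an assumed central-total correlation of 0.8-0.95 and on SDs and effects from 3-month Pea Pod changes, not 24-month DXA FM. The direction needs neither, because it follows from trunk FM being part of total FM. It also does not depend on which definition of central FM applies, since the skinfold index is absolute too. Only exploratory analyses are affected. Central FM remains a valid outcome as an amount of fat, and the primary Aim 1 test is untouched.

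**What to change.** In D7:
1. Keep absolute central FM in D7b and D7c and describe it as an amount of fat.
2. State that central FM is the DXA trunk measure of D5a, not the skinfold index of D5d.
3. Add one pre-specified exploratory distribution outcome from the same DXA regions, for example the log of trunk FM/(arm + leg FM), or central FM adjusted for total FM. Use the same DHA x GWG and DHA x gender terms in D7b, and the same DHA and DHA x time terms in D7c.
4. Base any statement about fat distribution on that outcome.

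The cost is a few sentences and one more run of models already planned. No new visit, scan or participant is needed. The downsides are one more exploratory outcome and, if the ratio is chosen, more noise when limb fat is low. The choice should be fixed before the dose assignments are released to the ancillary study team.

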The innovation of this application is in the unique utility of the potential findings. There is clearly a gap in knowledge and mixed directionality regarding the role of DHA to influence offspring body composition. This study will inform this critical gap and recommendations to women for DHA consumption. In addition, this grant proposal is innovative by proposing to solve a problem in new ways. The role of DHA in cognitive development is clear but DHA's role in obesity prevention is unknown. This proposal will move the body of knowledge forward and could *change* recommendations for the dose of prenatal DHA supplementation.

C) **Overview of the parent trial (ADORE)**: Section C provides an overview for the parent trial. The parent study has already received NIH funding and Human Subject Committee approval (Title: "*Docosahexaenoic acid (DHA) supplementation in pregnancy to reduce early preterm birth*" (ADORE); R01 HD83292-01 R01). The next sections (C1a-C1f) provide information on the approved and funded study. Drs. [name] and [name] are PIs on the parent study and both are Co-Is on this ancillary proposal. Study recruitment began June 2016 with the first delivery in November 2016. The proposed sample size is n=1200 with enrollment of 400 pregnant women at each of three sites (Kansas City, KS, Columbus, OH, and Cincinnati, OH). In this ancillary proposal, we are planning to follow offspring at the Kansas City site only. The primary purpose of the parent trial is to determine if prenatal DHA supplements of 1000 mg/d vs. 200 mg/d during the last two trimesters of pregnancy can reduce early pre-term birth (ePTB;

Specific Aim 1) and to conduct a secondary pregnancy efficacy analysis to determine if there is a subset of pregnancies most likely to benefit from DHA supplementation (Specific Aim 2). To obtain information about the effects of DHA on inflammation, sRAGE will be measured, which is plausibly influenced by DHA supplementation based on a murine model of LPS-induced inflammation (Specific Aim 3). Maternal and cord blood will be banked and available for future evaluations beyond fatty acid analysis. Budget constraints prevented including analysis in this ancillary proposal to explore the potential mechanisms for the influence of DHA on offspring body composition. However, the study team plans to use stored samples to conduct these studies.

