D3) **Recruitment for the current proposal**: Our study will enroll subjects from the RCT; "*Docosahexaenoic acid (DHA) supplementation in pregnancy to reduce early preterm birth*" (NIH R01 HD83292-01; n=1200 at 3 study sites). The current ancillary grant proposes to follow offspring from the Kansas City site where the expected enrollment will reach ~n=600. The parent study partnered with Juntos to recruit Hispanic pregnant women and they have been highly successful in recruiting a large number of Hispanic pregnant women, whom only speak Spanish. The GAINS study must be able to recruit the offspring born to this population. Enrollment may occur at any of the 4 time points: 2 weeks, 6 months, 12 months, or 24 months. If parents decide not to participate when contacted by study personnel, but agree to be contacted when the infant is older, the study personnel will contact them at 24 months.

The parent study (ADORE) is a Phase III Double Blinded Randomized Controlled Clinical Trial where women will be randomized to either a low or high dose DHA (1,000 mg/d or 200 mg/d). The primary outcome of this RCT is to move early pre-term birth to late pre-term birth. No targeted recruitment of women at risk for pre-term birth will be done (see **Table 1** for inclusion/exclusion criteria). Anyone meeting the inclusion criteria will be enrolled. At enrollment of the parent RCT, all participants will be asked if they can be contacted for other related studies. Their decision is recorded in the consent and a database. Late in pregnancy, women enrolled in the RCT will be approached. Based on [name] prior KUDOS RCT pregnancy supplementation study, the number enrolled was 350 with 86% of the sample retained at birth for follow up in the postnatal period. The study team has full confidence the recruitment goal can be met (see c7a "Power calculations" and D9 "Study Challenges" for further discussion).

Recruitment process: Both parents must give their permission unless one parent is deceased, unknown, incompetent, or not reasonably available, or when only one parent has legal responsibility for the care and custody of the child. If only one parent is signing, the reason will be well documented in the subject's chart/source documentation. Both signatures will be

obtained prior to any research procedures taking place on the child. One or both parent signatures may be obtained via REDcap as long as:

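### The exploratory longitudinal model in D7c offers gestational age at birth and infant diet as confounders, although both arise after randomisation and DHA may change the first

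*Combined protocol and SAP*

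**What the plan says.** D7c introduces the longitudinal model as an addition to the main tests: "Additionally, we will perform a linear mixed model to explore differences between the high vs. low supplement groups for infant FM and distribution". DHA group, time and their interaction are fixed effects, with a random subject effect.

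On covariates it says "We will use exploratory analyses to investigate, in a univariate fashion, covariates", and continues "GWG and infant gender will be included as well as other potential covariates". The list that follows ends with "maternal diet, infant diet, infant age at test, gestational age at birth, and socioeconomic status". The section closes: "We will analyze the data without confounding variables and repeat the analysis with confounding variables".

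It gives no retention rule and no final covariate set, and it does not say which of the two versions is to be read as the DHA effect.

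Elsewhere the protocol describes what the parent trial is for. Section C says it tests whether "1000 mg/d vs. 200 mg/d during the last two trimesters of pregnancy can reduce early pre-term birth". Section D3 says "The primary outcome of this RCT is to move early pre-term birth to late pre-term birth".

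**The concern.** Dose is randomised, so a confounder of the DHA effect would have to be something that could influence assignment. A variable fixed after assignment cannot do that; it can only be a consequence of treatment, or share causes with the outcome. By listing gestational age at birth and infant diet as confounders, D7c carries a habit suited to the observational pilot in D2, which compared unsupplemented women by measured DHA status, into a randomised comparison.

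Adjusting for gestational age does two things if DHA moves it. It takes out whatever part of the DHA effect on fat mass runs through the length of gestation. It can also create a difference where there is none, when an unmeasured factor affects both gestation and fat mass.

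At stake is the reading of the adjusted longitudinal result. If it differs from the unadjusted one, a reader cannot tell whether the gap reflects precision, baseline imbalance, or removal of part of the effect under study.

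**Working it through.** **Timing of each variable relative to assignment**

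- Assignment: on enrolment at 12 to 20 weeks of gestation (C1a, Table 1, C1e).
- Gestational age at birth: fixed at delivery, so after assignment. Sections C and D3 make the timing of birth the parent trial's target.
- Infant diet: recalls at each visit and a feeding questionnaire at 6 and 12 months (D5e), so after assignment. No section says that DHA changes it.
- GWG: from self-reported pre-pregnancy weight to the last clinic weight before delivery (D5b), so partly after assignment. No section says that DHA changes it.
- Pre-pregnancy BMI, maternal age, parity, education and socioeconomic status: maternal characteristics treated here as fixed before assignment.
- Maternal diet: listed without a measurement time.

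**A possible link from gestation to fat mass.** D2 names catch-up growth as a risk factor for greater offspring fat mass and describes preterm infants as likely to gain weight fast. The documents give no slope of fat mass on gestational age, and they give no DHA effect on mean gestation. No figure in the plan can therefore be reproduced, and what follows is an illustration.

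**Inputs**

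- n = 360 × (1 − 0.33) = 241, from the sample size and attrition in D7d.
- SD of fat mass = √[(549.9² + 622.4² + 640.7² + 539.3²)/4] = 590 g, from Table 2. This is 3-month change, used in place of 24-month fat mass.
- Assumed: SD of gestational age 1.8 weeks; DHA lengthens gestation by a = 0.1, 0.3 or 0.6 weeks; fat mass rises by b = 50 or 100 g per week of gestation.

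The check is a single-time-point regression with 3,000 simulated trials per row. The simulation standard error of an unadjusted mean is about (2 × 590/√241)/√3000 = 1.4 g.

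**Case 1: gestation lies on the path, with no direct effect.** Total effect = a × b. Expected adjusted estimate = 0.

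| a (weeks) | b (g/week) | total a × b (g) | unadjusted (g) | adjusted (g) |
|---|---|---|---|---|
| 0.1 | 50 | 5 | 4.4 | −0.6 |
| 0.1 | 100 | 10 | 11.9 | 1.6 |
| 0.3 | 50 | 15 | 14.2 | −0.7 |
| 0.3 | 100 | 30 | 31.8 | 1.4 |
| 0.6 | 50 | 30 | 29.8 | −0.1 |
| 0.6 | 100 | 60 | 62.6 | 2.5 |

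The unadjusted model recovers the total effect to within about 3 g. The adjusted one returns roughly zero. With a negative slope, as catch-up growth might suggest, the formula gives the same size with the opposite sign.

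**Case 2: a shared unmeasured cause, with no true DHA effect.** Assume one SD of that cause adds 1 week and 200 g. The shift is −a × 1 × 200/1.8² = −a × 61.7 g. That gives −6, −19 and −37 g for a = 0.1, 0.3 and 0.6. The simulated adjusted estimates are −7, −19 and −37 g; the unadjusted ones lie within 1 g of zero.

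**Case 3: DHA does not change gestation (a = 0).** Unadjusted −1.6 g, adjusted −1.5 g. There is no shift.

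**Would univariate investigation keep gestational age out?** If it were applied as a p < 0.05 screen, a rule the plan does not state, gestational age would be retained in 66% to 68% of the Case 1 runs at 50 g per week and in all of them at 100 g per week.

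**The case against.** The best defence is that the matter is contained. D7c is exploratory, the unadjusted model is run as well, and D7a and D7b use ANOVAs that do not draw on this list. All of that stands, and it limits the weight of the point.

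A second defence is that the analysed children are a consented single-site subset, enrolled at any of four ages, with 33% attrition allowed and a parent trial that adapts its allocation. Balance is not assured, so an adjusted analysis is reasonable. This also stands, but it argues for adjusting for variables fixed before assignment, not for one the treatment is meant to move.

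Third, age at test is also measured after randomisation. It describes when the scan was taken on a schedule counted from birth, and the documents give no route from DHA to it.

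A reader might go further in four ways that the documents do not support:

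- *That the univariate step is a defined selection on the outcome.* D7c states no threshold and no retention rule, and its list could be read as fixed. For the same reason, no probability of a false inclusion can be attached to it.
- *That such screening makes the standard errors too small.* Simulated p < 0.05 outcome screens, with covariates unaffected by treatment and n from 120 to 360, gave ratios of mean standard error to empirical SD of 0.98 to 1.01 and type I error of 4.6% to 5.6%. The effect is negligible.
- *That GWG should come out too.* Aim 1 is the DHA-by-GWG interaction, and the closing paragraph of A9 frames the question as the DHA effect with excess GWG controlled. Removing GWG would change the study's question.
- *That DHA alters infant diet.* For that variable the case rests on timing alone, and the parent trial is double-blind.

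**Conclusion.** The point holds for the adjusted version of the D7c model only. Gestational age at birth should not be presented as a confounder there, because the parent trial is designed to test whether DHA changes it. Infant diet shares the timing problem with weaker support.

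The adjusted estimate departs from the total DHA effect only if DHA changes the covariate and the covariate, or a shared cause, relates to fat mass. Under the assumed ranges the departure is 5 to 60 g along the path and 6 to 37 g through a shared cause. Against the 472 g pilot difference quoted in D2, 5/472 is about 1% and 60/472 about 13%; that pilot figure is a 3-month change by DHA status, so it is only a yardstick. These sizes rest on the assumptions, and so does their direction. A reader might infer that the trial's main conclusion is biased; it is not, since it comes from the D7a contrast. This is a low-cost improvement to an exploratory analysis.

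**What to change.** In D7c, replace the sentence on univariate investigation with a fixed adjusted set: pre-pregnancy BMI, maternal age, parity (now listed twice), education and socioeconomic status, plus infant sex and age at test. Keep GWG as the study's planned factor or effect modifier. Show gestational age at birth and infant diet only in a separately labelled explanatory model, with a statement that its DHA coefficient is not the total effect of the supplement.

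This takes one or two sentences and no new data, and leaves the Aim 1 and Aim 2 tests as they are. It gives up the freedom to choose covariates after seeing the data, and some precision. Under the assumed slopes, gestational age explains (50 × 1.8/590)² = 2% to (100 × 1.8/590)² = 9% of the variance in fat mass. Omitting it would then enlarge the standard error of the DHA effect by about 1% (1/√0.977) to 5% (1/√0.907).
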